2.1 Study Objectives

To evaluate the efficacy, safety, and tolerability of 2 doses of ubrogepant (50 and 100 mg) compared to placebo for the acute treatment of a single migraine attack.

2.2 Clinical Hypotheses

1. At least 1 ubrogepant dose is superior to placebo in the acute treatment of migraine.
2. Ubrogepant is safe and tolerable.

3. Study Design

This multicenter, randomized, double-blind, placebo-controlled, parallel-group, single attack study will enroll approximately 1650 patients from approximately 100 centers in the United States. Patients will be randomized (1:1:1) to 1 of the following 3 treatment groups: placebo, ubrogepant 50 mg, or ubrogepant 100 mg.

Study participants will have up to 60 days to treat a single qualifying migraine attack of moderate or severe intensity at home. Patients unable to treat a qualifying migraine within this time will be discontinued from the study.

[REDACTED]

The planned efficacy assessments are rating of headache severity, absence or presence of migraine-associated symptoms, use of rescue medication, use of optional second dose, and

recurrence of headache pain. A list and description of each efficacy assessment is in [Section 6.1](#) and the efficacy analyses are presented in [Section 7.3.1](#).

[Redacted text block]

[Redacted text block]

[Redacted text block]

[Redacted text block]

3.1 Adjudication Committee and Data Safety Monitoring Board

An Adjudication Charter will be established and will describe the process for the blinded surveillance, monitoring, and adjudication by the Clinical Adjudication Committee of events of posttreatment elevations of ALT and/or aspartate aminotransferase (AST) ≥ 3 times the upper limit of normal (ULN) in the ubrogepant program. The purpose of this committee charter will be to provide a standardized process for the adjudication of data associated with these events in order to determine whether the elevation was related to ubrogepant.

An independent Data Safety Monitoring Board (DSMB) will also be established to review unblinded safety data and summary reports, identify any safety issues and trends, and make recommendations to the Sponsor, including modification or early termination of a trial, if emerging data show unexpected and clinically significant adverse events of treatment.

Details of the DSMB memberships, standard operational procedures for data monitoring/review, frequency of review, and other pertinent details will be provided in a separate DSMB Charter.

4. Study Population and Entry Criteria

4.1 Number of Patients

Approximately 1650 patients will be randomized (550 patients per arm) from approximately 100 centers in the United States.

4.2 Study Population Characteristics

This study will include adult patients with migraine with or without aura.

4.3 Inclusion Criteria

To be eligible to participate in the study, patients must meet the following criteria:

1. Written informed consent and patient privacy information (eg, Written Authorization for Use and Release of Health and Research Study Information) obtained from the patient prior to initiation of any study-specific procedures
2. Male or female patients ages 18 to 75 years, inclusive, at Visit 1
3. At least a 1-year history of migraine with or without aura consistent with a diagnosis according to the International Classification of Headache Disorders, 3rd edition, beta version ([ICHD-3 beta, 2013; Section 12.1.1](#))
4. Migraine onset before age 50
5. By history, the patient's migraines typically last between 4 and 72 hours if untreated or treated unsuccessfully and migraine episodes are separated by at least 48 hours of headache pain freedom
6. History of 2 to 8 migraine attacks per month with moderate to severe headache pain in each of the 3 months prior to Screening (Visit 1)

[REDACTED]

- 8. Be able to read, understand and complete the study questionnaires and eDiary.

4.4 Exclusion Criteria

Patients who meet any of the following criteria will not be eligible to participate in the study:

[Redacted]

- 2. Difficulty distinguishing migraine headache from tension-type or other headaches.

[Redacted]

- 4. Has taken medication for acute treatment of headache (including acetaminophen, nonsteroidal anti-inflammatory drugs [NSAIDs], triptans, ergotamine, opioids, or combination analgesics) on 10 or more days per month in any of the 3 months prior to Visit 1.

- 5. Has a history of migraine aura with diplopia or impairment of level of consciousness, hemiplegic migraine, or retinal migraine as defined by ICHD-3 beta (Section 12.1.1)

- 6. Has a current diagnosis of new persistent daily headache, trigeminal autonomic cephalgia (eg, cluster headache), or painful cranial neuropathy as defined by ICHD-3 beta (Section 12.1.1)

- 7. Required hospital treatment of a migraine attack 3 or more times in the 6 months prior to Visit 1.

[Redacted]

[REDACTED]

9. Has a chronic non-headache pain condition requiring daily pain medication (with the exception of pregabalin)

[REDACTED]

[REDACTED]

[REDACTED]

[REDACTED]

[REDACTED]

[REDACTED]

[REDACTED]

[REDACTED]

[REDACTED]

[REDACTED]

[REDACTED]

[REDACTED]

[REDACTED]

[REDACTED]

[REDACTED]

[REDACTED]

[REDACTED]

[REDACTED]

[Redacted]

[Redacted]

[Redacted]

[Redacted]

[Redacted]

[Redacted]

[Redacted]

[Redacted]

[Redacted]

[Redacted]

[Redacted]

[Redacted]

- 20. History of malignancy in the 5 years prior to Visit 1, except for adequately treated basal cell or squamous cell skin cancer, or in situ cervical cancer
- 21. History of any prior gastrointestinal (GI) conditions (eg, diarrhea syndromes, inflammatory bowel disease) that may affect the absorption or metabolism of investigational product (IP); patients with prior gastric bariatric interventions (eg, Lap Band) which have been reversed are not excluded
- 22. History of acute hepatitis within 6 months of Screening (Visit 1) or chronic hepatitis (including nonalcoholic steatohepatitis) or a positive result on anti-hepatitis A immunoglobulin M (IgM) antibody, hepatitis B surface antigen, or anti-hepatitis C antibody testing at Screening (Visit 1)

[Redacted]

[Redacted]

[Redacted]

[Redacted]

[Redacted]

[Redacted]

[Redacted]

[Redacted]

4.5 Permissible and Prohibited Medications/Treatments

4.5.1 Permissible Medications/Treatments

Medications which are not specifically prohibited are allowed; however, there may be clarifications and restrictions with certain medications.

The following medications are allowed during the study, but are prohibited within 48 hours prior to taking IP:

- any triptan
- any ergot derivative
- any opioid
- any NSAID
- any other form of analgesic (including acetaminophen)
- any antiemetic agent
- any proton pump inhibitor

The following medications are allowed during the study, but are prohibited within 24 hours prior to taking IP:

- any antacid
- any H₂ blocker

Examples of allowed but restricted medications listed above are displayed in [Attachment 12.2](#).

Aspirin up to 325 mg/day is allowed for cardiac prophylaxis.

Daily use of pregabalin is allowed.

Selective serotonin reuptake inhibitors (SSRI) or serotonin norepinephrine reuptake inhibitors (SNRI) will be permitted provided that treatment is stable for at least 60 days prior to screening (Visit 1) and continues without change in dose throughout the study. SSRIs and SNRIs may not be started during the study.

Standard migraine prophylactic medications (eg, beta-blocker, tricyclic antidepressant, topiramate, valproic acid, botulinum toxin) will be permitted provided that the treatment is stable for at least 30 days prior to Visit 1, and continues without change in dose throughout the study. Prophylactic medications may not be started during the study.

Therapy considered necessary for the patient's welfare may be given at the discretion of the investigator. If the permissibility of a specific medication/treatment is in question, please contact Allergan.

4.5.1.1 Acute Treatment /Rescue Medication

Medications for acute treatment of migraine listed above may be taken during the study within the parameters noted in [Section 4.5.1](#).

[REDACTED]

[REDACTED] For details regarding the requirements for treatment with rescue medication and optional second dose, please refer to [Section 5.6.3](#).

[REDACTED]

4.5.1.2 Definition of Females of (Non-)Childbearing Potential and/or Acceptable Contraceptive Methods

For purposes of this study, females will be considered of childbearing potential unless they are naturally postmenopausal (ie, no menses for 2 years) or permanently sterilized (ie, bilateral tubal ligation, bilateral salpingectomy, bilateral oophorectomy or hysterectomy).

For women of childbearing potential who may participate in the study, the following methods of contraception, if properly used, are generally considered reliable: hormonal contraceptives (ie, oral, patch, vaginal ring, injection, implant), male condom with intravaginal spermicide,

diaphragm or cervical cap with spermicide, intrauterine device, vasectomized partner, or sexual abstinence.

For males who may participate in the study, the following methods of contraception, if properly used, are generally considered reliable: post-bilateral vasectomy, barrier contraception, or sexual abstinence. Male participants must also refrain from donating sperm during the course of the study.

The investigator and each patient will determine the appropriate method of contraception for the patient during the participation in the study.

If a female becomes pregnant during the study, the investigator will notify Allergan immediately after the pregnancy is confirmed and the patient will be exited from the study after appropriate safety follow-up. The investigator will (1) notify the patient's physician that the patient was being treated with investigational drug ubrogepant, and (2) follow the progress of the pregnancy. The investigator must document the outcome of the pregnancy and provide a copy of the documentation to Allergan.

4.5.2 Prohibited Medications/Treatments

The following medications are prohibited 30 days prior to Visit 1 and throughout the study period:

- Strong and moderate cytochrome P450 3A4 (CYP3A4) inhibitors, including but not limited to: systemic (oral/IV) itraconazole, ketoconazole, fluconazole; erythromycin, clarithromycin, telithromycin; diltiazem, verapamil; aprepitant; cyclosporine; nefazodone; cimetidine; quinine; and HIV protease inhibitors
- Strong and moderate CYP3A4 inducers, including but not limited to barbiturates (eg, phenobarbital and primidone), systemic (oral/IV) glucocorticoids, nevirapine, efavirenz, pioglitazone, carbamazepine, phenytoin, rifampin, rifabutin, and St. John's wort
- Inhibitors of the BCRP (breast cancer resistance protein) transporter (eg, rifampicin)
- Drugs with narrow therapeutic margins (eg, digoxin, warfarin)

Examples of prohibited medications in the classes noted above are displayed in [Section 12.2](#).

The decision to administer a prohibited medication/treatment is done with the safety of the study participant as the primary consideration. When possible, Allergan should be notified before the prohibited medication/treatment is administered.

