Study Objective: To evaluate the efficacy, safety, and tolerability of 2 doses of ubrogепant (50 mg and 100 mg) compared to placebo for the acute treatment of a single migraine attack

Clinical Hypotheses:

1. At least 1 ubrogепant dose is superior to placebo in the acute treatment of migraine.
2. Ubrogепant is safe and tolerable.

Study Design

Structure: Multicenter, randomized, double-blind, placebo-controlled, parallel-group, single attack study; randomization to placebo, ubrogепant 50 mg, or ubrogепant 100 mg.

Duration: The study includes a screening period of up to 14 days prior to randomization, a 60-day period in which to treat a single migraine attack, and a 4-week follow-up period.

Study Treatment Groups: Ubrogепant 50 mg, ubrogепant 100 mg

Controls: Ubrogепant placebo

Dosage/Dose Regimen: Study participants will have up to 60 days to treat a single qualifying migraine attack of moderate or severe headache pain intensity at home. Patients have the option to take a second dose of investigational product (IP) or rescue medication if the patient has either a nonresponding migraine or a migraine recurrence.

[REDACTED]

[REDACTED]

[REDACTED]

Study Population Characteristics

Number of Patients: Approximately 1650 patients will be randomized (550 per treatment arm)

Condition/Disease: Migraine with or without aura

Key Inclusion Criteria: To be eligible for study participation, patients must be 18 to 75 years of age (inclusive), have a history of migraine with or without aura for at least 1 year consistent with a diagnosis according to the International Classification of Headache Disorders criteria, 3rd edition, beta version (ICHD-3 beta, 2013) and experience between 2 to 8 migraine attacks with moderate to severe headache pain in each of the 3 months prior to Screening (Visit 1).

Key Exclusion Criteria: [REDACTED]

Response Measures

Efficacy: Rating of headache severity, absence or presence of migraine-associated symptoms, use of rescue medication, use of optional second dose, and recurrence of headache pain

[REDACTED]

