12.2 Examples of Prohibited Medications

Prohibited Medications

The following medications are prohibited 30 days prior to Screening and throughout the study period:

	Strong/Moderate CYP3A4 Inducers	Strong/Moderate CYP3A4 Inhibitors
Antidepressant/ Antianxiety	Barbiturates 
 • Amobarbital (Amytal[®]) • Aprobarbital (Alurate[®]) • Butalbital (Fiorinal[®], Fioricet[®]) • Butobarbital (Busodium[®], Butisol[®]) • Mephobarbital (Mebaral[®]) • Pentobarbital (Nembutal[®]) • Phenobarbital (Luminal[®], Solfoton[®]) • Secobarbital (Seconal[®]) 	Nefazodone (Serzone [®])
Antiseizure	Carbamazepine (Atretol [®] , Carbatrol [®] , Epitol [®] , Equetro [®] , Tegretol [®]) Oxcarbazepine (Trileptal [®]) Phenytoin (Dilantin [®] , Phenytek [®]) Primidone (Myidone [®] , Mysoline [®])	
Diabetes	Pioglitazone (Actos [®]) Troglitazone (Rezulin [®] , Resulin [®])	
Antiemetic		Aprepitant (Emend [®])
Antihypertension		Diltiazem (Cardizem [®]) Verapamil (Calan [®] , Calan SR [®])
Glucocorticoid (Systemic)	Betamethasone (Celestone [®]) Dexamethasone (Baycadron [®] , DexPak [®]) Hydrocortisone (Cortef [®]) Methylprednisolone (Medrol [®]) Prednisolone (Prelone [®]) Prednisone (Deltasone [®]) Triamcinolone (Kenalog [®])	
Antibiotics	Rifabutin (Mycobutin [®]) Rifampicin/ Rifampin (Rifadin [®] , Rifater [®] , Rimactane [®])	Erythromycin (Benzamycin [®] , EryTab [®]) Clarithromycin (Biaxin [®]) Telithromycin (Ketek [®])
Antifungal		Fluconazole (Diflucan [®] , Trican [®]) Itraconazole (Sporanox [®]) Ketoconazole (Nizoral [®])
Anti-HIV	Efavirenz (Stocrin [®] , Sustiva [®]) Nevirapine (Viramune [®])	Indinavir (Crixivan [®]) Nelfinavir (Viracept [®]) Ritonavir (Norvir [®]) Saquinavir (Fortovase [®] , Invirase [®])
Immunosuppressant		Cyclosporine - oral/IV only (Neoral [®] , Sandimmune [®])
Other	St John's Wort Enzalutamide (Xtandi [®]) Modafinil (Provigil [®])	Buprenorphine (Cizol [®] , Subutex [®] , Suboxone [®]), Quinine, armodafinil (Nuvigil [™])

Drugs with Narrow Therapeutic Margins	Warfarin (Coumadin [®]) Digoxin (Digitek [®] , Lanoxin [®] , Digox [®]) Cisapride (Prepulsid [®] , Propulsid [®]) Pimozide (Orap [®])
----------------------------------------------	-------------------------------------------------------------------------------------------------------------------------------------------------------------------------------------------------------------------

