The following medications are allowed during the study; however, they are prohibited within 48 hours prior to taking IP:

Triptan	Almotriptan (Axert [®]) Eletriptan (Relpax [®]) Frovatriptan (Frova [®]) Naratriptan (Amerge [®]) Rizatriptan (Maxalt [®]) Sumatriptan (Imitrex [®]) Zolmitriptan (Zomig [®])
Ergot Derivative	Dihydroergotamine (DHE 45 [®] , Migranal [®]) Ergotamine (Cafergot [®] , Ergomar [®] , Wigraine [®])
Opioid	Tramadol (eg, Ultracet [®] , Ultram [®]) Butorphanol (Stadol [®]) Codeine-containing analgesics (eg, Tylenol with Codeine #3 [®]) Hydrocodone (Zohydro ER [™])/Hydrocodone-containing analgesics (eg, Vicodin [®]) Oxycodone (Oxycontin [®] , Roxicodone [®])/Oxycodone-containing analgesics (eg, Percocet [®]) Morphine (MS Contin [®])
NSAID	Aspirin Combination medicines with NSAIDs (eg, Excedrin [®]) Diclofenac (Arthrotec [®] , Cataflam [®] , Voltaren [®]) Ibuprofen (eg, Advil [®] , Excedrin IB [®] , Motrin [®]) Ketoprofen (eg, Orudis [®]) Naproxen (eg, Aleve [®] , Naprosyn [®])
Analgesic	Acetaminophen (eg, Tylenol [®] or any combination drug Tylenol [®])
Antiemetic agent	Chlorpromazine (Thorazine [®]) Hydroxyzine (Vistaril [®]) Metoclopramide (Reglan [®]) Ondansetron (Zofran [®]) Prochlorperazine (Compazine [®]) Promethazine (Phenergan [®] , Mepergan [®])
Proton Pump Inhibitor	Esomeprazole (Nexium [®]) Lansoprazole (Prevacid [®] , Zoton [®]) Omeprazole (Losec [®] , Prilosec [®] , Zegerid [®]) Pantoprazole (Pantoloc [®] , Pantozol [®] , Protonix [®] , Somac [®] , Zurcal [®]) Rabeprazole (Aciphex [®] , Pariet [®] , Rabecid [®])

The following medications are allowed during the study; however, they are prohibited within 24 hours prior to taking IP:

Antacid	Aluminum Carbonate Gel (Basaljel [®]) Aluminium Hydroxide (AlternaGEL [®] , Amphojel [®]) Aluminium Hydroxide and magnesium hydroxide (Maalox [®] , Mylanta [®]) Bismuth Subsalicylate (Pepto-bismol [®]) Calcium Carbonate (Alcalak [®] , Quick-Eze [®] , Rennie [®] , Rolaid [®] , Titalac [®] , TUMS [®]) Hydrotalcite (Talcid [®]) Magaldrate plus Simethicone (Pepsil [®]) Magnesium Hydroxide (Phillips' Milk of Magnesia [®]) Sodium Bicarbonate (Alka-Seltzer [®] , Bicarbonate of Soda [®])
H₂ Blocker	Famotidine (Pepcid [®]) Nizatidine (Axiid [®]) Ranitidine (Zantac [®]) Cimetidine (Tagamet [®])

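### Cimetidine is prohibited by name for the whole study in Protocol Section 4.5.2 and allowed by name, apart from the 24 hours before dosing, in Attachment 12.2

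*Protocol*

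**What the plan says.** Three places in the protocol bear on cimetidine.

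- **Section 4.5.2 (prohibited medications).** Drugs on this list are barred from 30 days before Visit 1 and for the whole study. The bullet on strong and moderate CYP3A4 inhibitors ends with "nefazodone; cimetidine; quinine; and HIV protease inhibitors". The section then refers the reader to Section 12.2 for examples of its prohibited classes.
- **Attachment 12.2, last table.** Under the heading "The following medications are allowed during the study; however, they are prohibited within 24 hours prior to taking IP", the H2 blocker row has four entries, one of which is "Cimetidine (Tagamet" with its trade-name mark.
- **Section 4.5.1 (permissible medications).** Under "The following medications are allowed during the study, but are prohibited within 24 hours prior to taking IP", it covers H2 blockers as a whole class and makes no exception for cimetidine. It opens with the general statement "Medications which are not specifically prohibited are allowed". Its closing paragraph, beginning "If the permissibility of a specific medication/treatment is in question", tells sites to contact the sponsor.

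The first table of Attachment 12.2 has a column headed "Strong/Moderate CYP3A4 Inhibitors" for drugs barred throughout. Cimetidine is not in it.

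**The concern.** A coordinator checking a participant's medication gets a different answer depending on which page is open. Section 4.5.2 makes any cimetidine use in the study a breach. The attachment makes it acceptable outside the 24 hours before IP.

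The attachment is the natural page for looking up a drug by name. Someone who finds cimetidine there as allowed has no reason to ask the sponsor. A participant could then take a drug that the protocol elsewhere bars as a CYP3A4 inhibitor, which could bear on that person's drug exposure and safety. The same use could also be recorded as a deviation at one site and as permitted at another.

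Two things are not at stake. The wording is the same for all three arms of a randomised, double-blind trial, so no bias in the coprimary comparisons is suggested. Nor is an effect on eligibility claimed, because many of the exclusion criteria in Section 4.4 are redacted.

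**Working it through.** This is mainly a comparison of texts; the plan gives no figure of its own to reproduce.

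**1. The two rules side by side**

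| Source | Status of cimetidine | Period barred |
|---|---|---|
| Section 4.5.2 | prohibited, by name | 30 days before Visit 1, then the whole study |
| Attachment 12.2, H2 blocker row | allowed, by name | 24 hours before IP |
| Section 4.5.1 | allowed, as a member of the H2 blocker class | 24 hours before IP |

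All of this is current text, and none of these entries is redacted. The visible Amendment 2 entries for Sections 4.5.1 and 12.2 deal with proton pump inhibitors, systemic glucocorticoids and armodafinil. None deals with cimetidine.

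**2. Is cimetidine a lone exception?**

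Section 4.5.2 names 13 inhibitors individually: itraconazole, ketoconazole, fluconazole, erythromycin, clarithromycin, telithromycin, diltiazem, verapamil, aprepitant, cyclosporine, nefazodone, cimetidine and quinine. HIV protease inhibitors are named only as a class and are not counted.

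- Found in the inhibitor column of Attachment 12.2: 12.
- Not found: 13 − 12 = 1, which is cimetidine.
- H2 blockers named as allowed in the attachment: 4 (famotidine, nizatidine, ranitidine, cimetidine). Only cimetidine is also named in Section 4.5.2.

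The column gives examples, so a missing name is not an error in itself. Its effect is that the row of allowed drugs is the attachment's only entry for cimetidine.

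**3. How the attachment handles another overlap**

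Aprepitant is labelled an antiemetic in the attachment, and Section 4.5.1 allows antiemetics as a class with a 48-hour restriction. The attachment lists aprepitant in the prohibited inhibitor column and leaves it out of the allowed antiemetic row. Cimetidine gets the reverse treatment.

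**4. Length of each rule**

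Inputs: 30 days before Visit 1 (Section 4.5.2); up to 14 days of screening, then "a 60-day period in which to treat a single migraine attack, and a 4-week follow-up period" (Protocol Summary, Duration). Four weeks is taken as 28 days.

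Period under Section 4.5.2 = days before Visit 1 + screening + time to treat + follow-up.

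- Maximum: 30 + 14 + 60 + 28 = 132 days.
- Minimum: 30 + 0 + 0 + 28 = 58 days. This assumes that screening, randomisation and dosing fall on one day, so it is a floor and not a typical value.
- From Visit 1 onward only: 28 to 102 days (58 − 30 and 132 − 30).

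Period under Attachment 12.2: 24 hours before IP. Both rules bar the drug in those 24 hours; they disagree over the rest of the period.

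**The case against.** The strongest reply is that the body text already settles the matter. Section 4.5.1 allows only what is not specifically prohibited, so a named prohibition outranks a class permission, and the handling of aprepitant fits that reading. The attachment is presented as examples of the body-text rules. On this view the defect is one drug name in one row.

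Much of this stands. The general allowance for H2 blockers in Section 4.5.1 can be read as subject to Section 4.5.2, and on its own it would not be a firm contradiction. It does not dispose of the attachment entry, which allows cimetidine by name. Both entries are specific, and nothing ranks one above the other. The instruction to contact the sponsor applies when permissibility is in doubt, and a plain entry as allowed raises no doubt.

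A second line concerns consequence. This is a single-attack study with one initial dose and an optional second. Both rules cover the 24 hours before IP. The mITT and Safety populations exclude nobody for prohibited medication, and the SAP's table of analysis populations has no per-protocol set. Sites also review prohibited medications with patients (Section 8.5) and ask about medication changes at each visit (Section 8.7). All of that is correct, and it limits the point to trial conduct, individual safety and deviation reporting. It does not tell a site which rule to apply when it makes those checks.

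A third line is that the 30 days before Visit 1 matter only at entry. The range from Visit 1 onward, 28 to 102 days, is given above for that reason. The 58 to 132 days describe the Section 4.5.2 rule as written.

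**Conclusion.** The concern holds. The current protocol prohibits cimetidine by name in one place and allows it by name in another. The rules differ widely in length: 58 to 132 days under Section 4.5.2 (28 to 102 from Visit 1) against 24 hours before IP under Attachment 12.2. The lower ends assume no elapsed time in screening or before the treated attack; the upper ends assume the full 14 and 60 days.

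The practical effect cannot be sized, because the documents give neither the number of participants likely to use cimetidine nor the magnitude of any interaction. Power, type I error and the coprimary analyses are unaffected. The matter should be corrected because sites must apply this rule to participants. Which rule is clinically right is not a question for this review.

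**What to change.** Reconcile Section 4.5.1, Section 4.5.2, the inhibitor column of Attachment 12.2 and its H2 blocker row, so that cimetidine falls under one rule stated the same way throughout. The sponsor's clinical team should choose the rule.

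Then notify sites, and confirm that the Protocol Deviation Requirement Specification cited in SAP Section 5.1.1.2.3 uses the same rule. That document is not among those available here and may already do so.

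The cost is a one-line protocol clarification, a site memo and a check of one line in the deviation specification. No analysis, table or sample size changes.
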